#### **6.5 ANALYSIS OF TREATMENT PATTERNS**

Descriptive statistics will be used to tabulate characteristics of isavuconazole treatment at the index date, including setting of treatment administration, loading dose, and maintenance dose, administration mode, and therapy duration (Appendix 1, Analysis Table 12). Therapy duration will be calculated as the treatment modification date minus the isavuconazole initiation date among patients noted to have a frequency decrease and a frequency for initial treatment of every 8 hours. Treatment patterns during the post-index period also will be summarized with descriptive statistics. Characteristics related to treatment modification will include whether the modification occurred, days between index treatment and treatment modification, type and reason for therapy modification, and summaries of patients discharged from the hospital with an isavuconazole prescription (Appendix 1, Analysis Table 13). Days between index treatment and treatment modification will be calculated as the date of first modification minus the date of isavuconazole initiation for patients who did not receive a loading dose and as the date of the second modification minus the date of the first modification for patients who did receive a loading dose.

Similar descriptive summaries will be provided for treatment patterns in the post-index period related to combination therapy (Appendix 1, Analysis Table 14), therapeutic drug monitoring (Appendix 1, Analysis Table 15), isavuconazole discontinuation (Appendix 1, Analysis Table 16), and switching to a new antifungal agent (Appendix 1, Analysis

PFIZER CONFIDENTIAL

CT24-WI-GL03-RF03 1.0 *Non-Interventional Statistical Analysis Plan For Secondary Data Collection*  
Study 16-Sep-2020  
Page 16 of 19

Table 17). Characteristics to be summarized will include occurrence of each item, days from isavuconazole initiation to the occurrence of each item, and other item-specific details among patients who experienced each item.

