- **Pre-index event period:** Baseline data on demographics and medical history will be collected based on all available information in medical records before the index event.
- **Post-index event period:** The timeframe for follow-up data collection will begin one day post-index treatment initiation and end at the earliest of the following: six-months post-index treatment discontinuation, death, loss to follow-up, or December 31, 2019. Key timepoints of interest for assessment of clinical outcomes (mortality and overall response), and safety will be assessed at 6 weeks, 12 weeks, and 24 weeks after initiation of index treatment.

Variables: Categories to be abstracted from the medical records if available include, but are not limited to, the following:

- Demographic, medical history, and clinical characteristics (eg, age, sex, history of invasive fungal infection and prior antifungal treatments, fungal disease characteristics such as diagnosis, mycological confirmation, date of diagnosis, and other comorbidities including underlying illness/risk factors for invasive aspergillosis and mucormycosis).
- Clinical outcomes (eg, overall response [including clinical response, mycological response, radiological response], and mortality).
- Safety outcomes (AEs and SAEs).
- Isavuconazole treatment patterns (eg, formulation, dosage [loading and maintenance], duration, treatment changes (including dosage adjustments, switching, and discontinuation), and concomitant medication).
- Health care resource utilization (eg, length of stay [LOS], emergency room [ER] visits, intensive care unit [ICU] visits and LOS, inpatient hospitalizations, and planned and unplanned outpatient visits).

Study size: Precision estimates were generated based on the all-cause mortality rate at day 42 for patients with invasive aspergillosis who received isavuconazole in the SECURE trial.⁴ A sample size of 150 to 200 patients is expected to yield a reasonable margin of error (between 5.00% and 6.25%) for estimating a 95% confidence interval (CI) for the mortality

^d The eligibility period end date is subject to change based on timing of medical record abstraction and anticipated number of potentially eligible patients during the proposed eligibility timeframe.

rate. However, 95% CIs may be wider for analyses of rare events or analyses conducted in small subgroups.

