9.4.2. Isavuconazole Treatment Patterns

Category	Variable	Timepoint
Index treatment (isavuconazole) administration	
Setting of treatment administration:
 
 • Inpatient setting: 
 • Oncology ward; • Hematology ward; • Transplantation ward; • ICU; • General medicine ward; • Other ward (specify). • Outpatient setting; • Other (specify); • Unknown. 	Index date, post-index period
	
Loading-dose method of administration:
 
 • Infusion; • Oral; • Unknown; • Not applicable. 	
	
Date of first loading-dose administration (DD MMM YYYY)
	
	
Date of last loading-dose administration (DD MMM YYYY)
	
	
Loading dose:
 
 • 372 mg of isavuconazonium sulfate; • Other (specify). 	
	
Loading-dose frequency:
 
 • Every 8 hours for 48 hours (ie, 6 doses); • Other (specify). 	
	
Maintenance therapy method of administration:
 
 • Infusion; • Oral; • Maintenance therapy not administered; • Unknown; • Not applicable. 	
	
Date of first dose of maintenance therapy (DD MMM YYYY)
	
	
Date of last dose of maintenance therapy (DD MMM YYYY)
	
	
Maintenance dose (mg):
 
 • 372 mg of isavuconazonium sulfate; 	

Category	Variable	Timepoint
	
 • Other (specify). 
Maintenance dose frequency:
 
 • Every 24 hours (ie, once daily); • Other (specify). 	
Modification of index treatment	
Treatment modification (eg, dose adjustment, mode of administration change):
 
 • Yes; • No; • Unknown. 	Post-index period
	
Date of index therapy modification (DD MMM YYYY)
 
Type of therapy modification (all that apply):
 
 • Change from infusion to oral capsule; • Change from oral capsule to infusion; • Dose increase; • Dose decrease; • Frequency increase; • Frequency decrease; • Other (specify); • Unknown. 	
	
Reason for index therapy modification:
 
 • Lack of response to treatment; • AE; • Patient decision (unrelated to AEs); • TDM; • Drug-drug interaction; • Other (specify); • Unknown. 	

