9.9.2.2. Analysis Plan for Secondary Objectives

Basic summaries of site and patient counts included in the study will be produced. Patients will be characterized by fungal disease type (invasive aspergillosis or mucormycosis) at the time of isavuconazole initiation, in terms of demographics, disease characteristics, medical history, treatment history, prognostic factors, and other factors which may be predictive of clinical outcome.

For isavuconazole treatment patterns, descriptive statistics will be used to summarize details of isavuconazole administration (eg, location, therapy duration, loading dose and frequency, and maintenance dose and frequency), modifications to index therapy, details of therapeutic drug monitoring (therapeutic drug monitoring [TDM], eg, assay type, outcome), discontinuation, switching, antibiotic use before and after index therapy, and concomitant medication.

Health care resource utilization during the post-index period will be reported at 6 weeks, 12 weeks, and 24 weeks after initiation of index therapy. HCRU will include counts and proportions of patients with inpatient visits, outpatient visits, ICU admissions and ER visits and use of mechanical ventilators. Reason for visits and duration of visits will be described. Inpatient LOS and ICU LOS will be derived using admission and discharge dates.

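### SAP 6.5 computes therapy duration as the length of the loading phase (about 2 days), and its days-to-modification row uses a later origin for loaded patients

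*SAP*

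**What the plan says.** SAP 6.5 deals with treatment length in three places.

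- **Table 12** summarises "characteristics of isavuconazole treatment at the index date", and therapy duration is among the items. The rule is: "Therapy duration will be calculated as the treatment modification date minus the isavuconazole initiation date among patients noted to have a frequency decrease". The sentence then limits the calculation to patients whose starting frequency was every 8 hours.
- **Table 13** gives the days between index treatment and treatment modification. Patients with no loading dose are counted from initiation to the first modification. For the others the value is taken "as the date of the second modification minus the date of the first modification for patients who did receive a loading dose".
- **Tables 14 to 17** (combination therapy, drug monitoring, discontinuation, switching) give the occurrence of each item and "days from isavuconazole initiation to the occurrence of each item, and other item-specific details among patients who experienced each item". Discontinuation is Table 16.

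In Protocol 9.4.2 the listed loading frequency is "Every 8 hours for 48 hours (ie, 6 doses" and the listed maintenance frequency is "Every 24 hours (ie, once daily"; each also has an open 'other' option. The variable list in the protocol abstract includes "formulation, dosage [loading and maintenance], duration, treatment changes". Protocol 9.9.2.2 plans summaries of "details of isavuconazole administration (eg, location, therapy duration, loading dose and frequency, and maintenance dose and frequency". Both treat duration as an item distinct from loading and maintenance dosing.

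**The concern.** A patient who starts every 8 hours and then has a frequency decrease has, on the listed schedule, simply moved from loading to maintenance. The time to that step says nothing about how long the patient was treated. Patients who did not start every 8 hours, or who have no recorded frequency decrease, get no value.

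Treatment patterns are a secondary objective, and therapy duration is one of the protocol's example items for it. A Table 12 row that carries that name with values near 2 days could be read as length of treatment.

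Table 13 has a related problem. Its label says the count starts at index treatment, but for loaded patients it starts at the first modification. Loaded and unloaded patients are then summarised in one row with different starting points.

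**Working it through.** **Inputs.** Loading schedule of 6 doses, 8 hours apart, then once daily (Protocol 9.4.2). Intervals are differences between two calendar dates, in days (SAP 6.1). Rules for Tables 12, 13 and 16 from SAP 6.5.

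**Step 1: the plan's own figure.** 6 × 8 h = 48 h = 2.0 days, which agrees with the 48 hours listed in Protocol 9.4.2.

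**Step 2: what the Table 12 rule returns.** The calendar difference is the whole number of days in (clock hour of first dose + hours to the modification). Taken over all 24 starting hours:

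| Date recorded as the modification | Hours after first dose | Result (days) | Mean |
|---|---|---|---|
| Last loading dose | 40 | 1 to 2 | 1.67 |
| End of the 48 hours | 48 | 2 | 2.00 |
| First once-daily dose, 24 h after the last loading dose (assumption) | 64 | 2 to 3 | 2.67 |

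The result is about 2 days, range 1 to 3, and does not depend on course length.

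**Step 3: compared with the whole course.** For assumed courses of 14, 42, 84 and 168 days, 2 days is 2/14 = 14.3%, 2/42 = 4.8%, 2/84 = 2.4% and 2/168 = 1.2% of the course.

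**Step 4: Table 13.** Assume the step-down is recorded as the first modification, on day 2. A change t days after initiation is then reported as t in an unloaded patient and t − 2 in a loaded one.

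| t (days) | Unloaded | Loaded | Shortfall |
|---|---|---|---|
| 7 | 7 | 5 | 2/7 = 29% |
| 14 | 14 | 12 | 2/14 = 14% |
| 28 | 28 | 26 | 2/28 = 7% |

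The pooled mean is short by 2 × the loaded fraction. With assumed fractions of 0.50, 0.80 and 0.95 this is 1.0, 1.6 and 1.9 days.

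**Step 5: dependence on coding.** Protocol 9.4.2 has its own date fields for the first and last loading dose and the first maintenance dose, apart from the treatment-modification fields. Neither document says that the planned step-down is entered as a modification. Where it is not, a loaded patient with one later change has no Table 13 value. A loaded patient with changes on days 7 and 28 would get 28 − 7 = 21 instead of 7. Table 12 would be blank or would pick up a later frequency decrease.

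**Step 6: Table 16.** Days from initiation to discontinuation is the whole-course length, for patients who discontinued. Protocol 9.4.2 also allows discontinuation to be recorded as no or unknown. SAP 6.5 gives no duration rule for those patients and does not tie this quantity to therapy duration.

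**The case against.** **Table 12 may be only a slip of wording.** The table describes treatment at the index date, and the every-8-hours restriction is stated openly, so a loading-phase item was probably intended. The Appendix 1 table shells are an embedded file that was not available; a row title or footnote there could already say so. This stands as an explanation, but the SAP text would still need correcting.

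**Whole-course length is not lost.** A reader might infer that the study never reports how long patients were treated. The documents do not support that. Table 16 supplies it for patients who stopped, the number who discontinued is tabulated, and Protocol 9.9.1 requires missing data to be counted for each variable. What is absent is the name and a rule for patients with no recorded stop.

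**The effect of the missing stops cannot be sized.** A reader might also infer a large downward bias. Under the December 31, 2019 limit in Protocol 9.3.1.3, someone started on June 30, 2019 and still treated at the limit has had 184 days of therapy and no Table 16 value. But the post-index definition in SAP 4.2 omits that limit and follows patients to six months after discontinuation, death or loss to follow-up. Death unrelated to therapy is a listed reason for discontinuation, so some deaths on treatment supply a stop. The number of patients without a stop is not given, and those lost early need not have long courses.

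**Table 13 has a coherent reading.** If the row means time from the start of maintenance, both groups share one origin and the planned step-down is properly left out. That reading makes this a mismatch of label and origin, not a wrong calculation. The label still says index treatment, and Tables 14 to 17 count from initiation.

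**The SAP may change the protocol's plans.** Protocol 9.9 allows this, and duration is given only as an example item. Calling this a protocol breach would go too far.

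**Conclusion.** The point holds and is minor. Followed as written, the Table 12 rule gives the loading-phase length (about 2 days, 1 to 3 by calendar dates) under the name of therapy duration, an item the protocol lists separately from dosing. Whole-course length exists only in Table 16, under another name and only for patients who discontinued. Table 13 values in loaded patients are about 2 days short of what the label says.

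The figure of 2 days assumes the listed 48-hour schedule; the Table 13 figure also assumes that the step-down is recorded as the first modification. Only descriptive rows under a secondary objective are affected: mortality, response and safety analyses do not use these intervals.

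**What to change.** In a revised SAP, before data collection is complete as Protocol 9.9 requires:

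1. Rename the Table 12 quantity loading-phase duration. Derive it from the loading-dose and first-maintenance-dose dates in Protocol 9.4.2, not from the modification field.
2. Define therapy duration as discontinuation or last-dose date minus initiation date, and cross-refer it to Table 16. Report patients with no recorded stop separately. Alternatively, censor them at end of follow-up, after reconciling the December 31, 2019 limit in Protocol 9.3.1.3 with SAP 4.2.
3. Count days to first modification from initiation in every patient, leaving out the planned loading-to-maintenance step even where it was entered as a modification. Otherwise, relabel the Table 13 row as time from start of maintenance.
4. Confirm that the EDC derives these intervals. Protocol 9.10 says it calculates durations and that no dates remain in the data set, so an interval not set up during collection may not be recoverable from that data set.

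The cost is small: one renamed row, one linked definition and one common origin or label. The protocol already lists the dates needed. The open item is the EDC check, since neither the CRF nor the table shells were available.

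### SAP 6.5 counts days to treatment modification from two different starting points, and sets the scheduled loading step aside only in that row and only by position

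*SAP*

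**What the plan says.** SAP 6.5 lists the content of Table 13: "Characteristics related to treatment modification will include whether the modification occurred", then the days from index treatment to modification, and the type and reason. For the days, patients without a loading dose get the first modification date minus the initiation date. Loaded patients get a different formula, "as the date of the second modification minus the date of the first modification for patients who did receive a loading dose".

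The same section defines a therapy duration for Table 12 as a modification date minus the initiation date, "among patients noted to have a frequency decrease and a frequency for initial treatment of every 8 hours". For Tables 14 to 17 (combination therapy, drug monitoring, discontinuation, switching) it uses "days from isavuconazole initiation to the occurrence of each item".

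Protocol 9.4.2 lists loading as six doses, one every 8 hours over 48 hours, and maintenance as once daily. The listed dose is "372 mg of isavuconazonium sulfate" in both phases. A frequency decrease is one of the modification types, and several types may be ticked on one record. Neither the types nor the reasons include a code for the scheduled step. SAP Table 1 counts any documented index treatment modification as an outcome. The table shells are in an Excel attachment to SAP Appendix 1 that cannot be read here.

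**The concern.** The loaded-patient formula makes sense only if the first modification record is the scheduled change from loading to maintenance. The SAP never says so. It removes that record by its place in the sequence, and it does so in one row. Two problems follow.

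First, the days row does not measure what its label says in loaded patients. It starts at the end of loading, or at whatever was recorded first, while in the other patients it starts at initiation.

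Second, the visible text does not carry the same set-aside over to occurrence, type and reason, or to the outcome in SAP Table 1. A loaded patient who simply followed the listed regimen could count as modified, with a frequency decrease, and yet have no value in the days row. The rows of one table would then describe different patients. At stake is the reading of Table 13: how often, and how soon, clinicians changed treatment.

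**Working it through.** The plan gives no figure on this point to reproduce. The inputs from protocol 9.4.2 are a loading interval of 8 hours for 48 hours, a maintenance interval of 24 hours, and 372 mg in both phases. As a check, 48 / 8 = 6 loading doses, which agrees with the protocol. Days 1, 3, 10 and 30 below are examples of mine.

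**What the scheduled step looks like as a record.** It falls at 48 / 24 = 2 days. The dose goes from 372 mg to 372 mg, so there is no dose change. The interval goes from 8 to 24 hours, which is a frequency decrease.

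**Whether the SAP expects it among the modifications.** The therapy-duration rule applied to this record gives 2 − 0 = 2 days, the length of loading. That rule needs the step to be stored as a dated modification, and the second-minus-first rule needs it to be the first one. This is an inference, but the two rules fit together in no other obvious way.

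**What the days row returns.**

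| Patient | Modification records (day) | SAP 6.5 value | First genuine change, from initiation |
|---|---|---|---|
| Not loaded, change on day 10 | 10 | 10 − 0 = 10 | 10 |
| Loaded, step recorded, change on day 10 | 2, 10 | 10 − 2 = 8 | 10 |
| Loaded, step recorded, nothing else | 2 | none | no genuine change |
| Loaded, route change ticked on the step's record | 2 | none | 2 |
| Loaded, route change on day 1, step on day 2 | 1, 2 | 2 − 1 = 1 | 1 |
| Loaded, step not recorded, change on day 10 | 10 | none | 10 |
| Loaded, step not recorded, changes on days 10 and 30 | 10, 30 | 30 − 10 = 20 | 10 |
| Loaded, step not recorded, changes on days 1 and 10 | 1, 10 | 10 − 1 = 9 | 1 |

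The second line is the case the SAP's rules imply, and the shift there is 2 days. In the fifth line the two numbers agree by coincidence: the rule has measured the time from the route change to the scheduled step, and a step dated day 3 would give 3 − 1 = 2. The last three lines arise only if a site did not enter the step.

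**Percentage modified.** Overstatement = (patients whose only modification record is the step) / (all patients). The documents do not give the numerator. It is zero if no site enters the step. Dose-change counts, route-change counts and the count for each named reason do not change. A recorded step would have its reason entered as other or unknown, or left blank.

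**The case against.** The strongest reply concerns what cannot be seen. SAP 6.1 sends table detail to Appendix 1, and the Table 13 shell may exclude the step from occurrence, type and reason. That stands: the point on those rows is conditional on the shell. It does not rescue the days row, whose formula is written in the body of SAP 6.5.

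Time from the end of loading to the next change is a coherent interval in itself. True, but it is not the interval the row names, and it is pooled with times counted from initiation.

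The SAP presupposes that sites enter the step, and protocol 9.6.1 has the CRO train the abstractors. So the larger errors in the table, from an unrecorded step, are the less likely case. That also stands. They are a risk, because protocol 9.4.2 lists loading and maintenance dates separately and a site could reasonably regard the transition as already captured.

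A reader could see part of the effect in the frequency-decrease row and in the number contributing to the Table 12 duration. That is fair, but the overlap with other modifications would not be visible.

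A reader might also infer that most patients will be reported as modified. If a share L is loaded, every step is recorded and a share m has a genuine change, the reported share is L + (1 − L)m. With L from 50% to 100% and m from 5% to 30%, it runs from 0.5 + 0.5 × 0.05 = 52.5% up to 100%. The documents give neither L nor m, nor the recording practice, so they do not support any such figure. Nor is this a departure from the protocol, which in section 9.4 leaves variable detail to the SAP.

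**Conclusion.** The point holds for the days row as written. It has two origins, about 2 days apart if the listed regimen was followed and the step is stored first. It also relies on record order, which gives a wrong or missing value whenever the first record is not the step alone. For occurrence, type and reason the visible SAP applies no matching exclusion. Whether those rows will include routine loading depends on the unseen shell and on site practice, and the size is unknown.

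The priority is minor. Treatment patterns are a secondary, descriptive objective, one table is affected, and mortality, response and safety are untouched. The conclusion rests on the inference that the first modification in loaded patients is meant to be the scheduled step.

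**What to change.** In SAP 6.5, define the scheduled loading-to-maintenance step by content:

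- the initial frequency was every 8 hours;
- the record is the first frequency decrease to the maintenance frequency;
- no unscheduled reason is given (lack of response, adverse event, patient decision, drug monitoring, drug-drug interaction).

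If another type is ticked on the same record, keep that type as a modification. Check the classification against the last-loading and first-maintenance dates where these were collected.

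Exclude the step so defined from occurrence, type, reason and timing alike. Compute days as the first remaining modification date minus the initiation date in all patients, the starting point already used for Tables 14 to 17. Show the transition as its own line in Table 12. Confirm that the Table 13 shell says the same.

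The cost is a few sentences and one derivation step, using items SAP 6.5 already relies on. Protocol 9.9 provides for a revised SAP before data collection is complete. There are two downsides: a few genuine decreases coded as other or unknown may be classed as scheduled, and loading at another frequency is not covered. Footnote the number of records excluded and the number of patients loaded at another frequency.
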